E-STIM	Electrical Nerve Stimulation
FCC	Federal Communication Commission
FDA	Food & Drug Administration
HIV	Human Immunodeficiency Virus
IENFD	Intraepidermal Nerve Fiber Density
IRB	Institutional Review Board
ITT	Intent to Treat
LCD	Liquid Crystal Display
LOPS	Loss of the Protective Sensation
LSA	Laser Sensor Assembly
MedDRA	Medical Dictionary for Regulatory Activities
NCS	Nerve Conduction Studies
NeuroQoL	Neuropathy and foot ulcer specific quality of life instrument
NOS	Nitric Oxide Synthase
NPRS	Numeric Pain Rating Scale
PAD	Peripheral Arterial Disease
PEMF	Pulsed Electromagnetic Field
PGI	Patient Global Impression
PRFE	Pulsed Radio Frequency Energy

PRN	As Needed
РТ	Physical Therapy
QA	Quality Assurance
QC	Quality Control
QST	Quantitative Sensory Test
SAE	Serious Adverse Event
SAP	Statistical Analysis Plan
SAS	Statistical Analysis System
SPP	Skin Perfusion Pressure
SSRI	Selective Serotonin Reuptake Inhibitors
SNRI	Serotonin-norepinephrine reuptake inhibitors
TCA	Tricyclic Antidepressants
UADE	Unanticipated Adverse Device Effect

1. INTRODUCTION AND BACKGROUND

In 2015 the Centers for Disease Control and Prevention (CDC) had estimated that 30.3 million people have diabetes (9.4% of the United States population), of which 23.1 million are diagnosed and 7.2 million are undiagnosed.¹ The most common form of diabetes mellitus, type 2 diabetes mellitus, is projected to affect an estimated 366 million people worldwide by 2030.² Diabetic neuropathies are the most prominent chronic complications of diabetes.³ While symptomatic or asymptomatic neuropathy can be diagnosed at any time during the course of the disease, there tends to be an increased association with increased age and disease duration.⁴ The maintenance of stable glycemic control has been associated with improvement in neuropathic pain for people with type 1 and type 2 diabetes. However, people with type 2 diabetes, despite adequate control, have a higher prevalence for developing diabetic distal symmetric peripheral neuropathy (DSPN).³

Clinical neuropathy syndromes associated with diabetes mellitus are categorized according to their neurologic distribution. While overlap in presentation exists the categories are as follows: ³

able 1. Classification for diabetic neuropathies		
A. Diffuse neuropathy	B. Mononeuropathy (mononeuritis multiplex)	
DSPN	(atypical forms)	
• Primarily small-fiber neuropathy	• Isolated cranial or peripheral nerve (e.g., CN III,	
 Primarily large-fiber neuropathy 	ulnar, median, femoral, peroneal)	
• Mixed small- and large-fiber neuropathy (most	 Mononeuritis multiplex (if confluent may 	
common)	resemble polyneuropathy)	
Autonomic		
Cardiovascular		
Reduced HRV	C. Radiculopathy or polyradiculopathy (atypical	
Resting tachycardia	forms)	
Orthostatic hypotension	• Radiculoplexus neuropathy (a.k.a. lumbosacral	
• Sudden death (malignant arrhythmia)	polyradiculopathy, proximal motor amyotrophy)	
Gastrointestinal	• Thoracic radiculopathy	
• Diabetic gastroparesis (gastropathy)		
• Diabetic enteropathy (diarrhea)		
Colonic hypomotility (constipation)		
Urogenital		
• Diabetic cystopathy (neurogenic bladder)		
• Erectile dysfunction	Nondiabetic neuropathies common in diabetes	
• Female sexual dysfunction	• Pressure palsies	
Sudomotor Dysfunction	• Chronic inflammatory demyelinating	
 Distal hypohydrosis/anhidrosis, 	polyneuropathy	
• Gustatory sweating	• Radiculoplexus neuropathy	
Hypoglycemia Unawareness	• Acute painful small-fiber neuropathies	
Abnormal Pupillary Function	(treatment-induced)	

Table 1. Classification for diabetic neuropathies

Diabetic distal symmetric peripheral neuropathy (DSPN) is the most common form of diabetic neuropathy and accounts for approximately 75% of diabetic neuropathies.³ Clinical presentation and clinical course of diabetic neuropathy varies in prevalence associated with both the duration of

disease and maintenance of adequate glycemic control. Corresponding to length dependent nerve damage, patients present with distal symptoms that progress proximally affecting the lower extremities more prominently than the upper extremities. Patients typically describe DSPN symptoms in terms of increased or decreased sensations resulting from damage of the myelinated and unmyelinated cutaneous nerve fibers.

The clinical presentation of DSPN initially involves the feet. DSPN leads to balance issues, causing fall and fractures. Initially affects smaller unmyelinated fibers which convey pain and unpleasant temperature sensations. With progression, larger myelinated fibers are affected and can be the cause of numbness, tingling, and insensate feet leading to diabetic foot ulceration (Table 2).³

Large myelinated nerve fibers	Small myelinated nerve fibers	
Numbness	Pain:	
Tingling	burning	
Poor balance	electric shocks	
	stabbing	

Table 2. Symptoms and Signs of DSPN*

*Adapted from Pop-Busui, R, Boulton, AJ. Diabetic Neuropathy: A Position Statement by the American Diabetes Association. Diabetes Care 2017 Jan; 40(1):139³

Diabetic neuropathy is a major cause of foot ulceration which is a complication that arises in late stages of DSPN which can lead to amputations and increased health economic costs.³ Microvascular compromise of smaller arterioles demonstrating endothelial dysfunction progressing to calcification, and dysfunction in larger vasculature, add to the complexity of the medical presentation, with overlapping syndromes of peripheral ischemia, that may or may not contribute to the lower extremity pain experienced by patients. Diabetic-related metabolic abnormalities may lead to an impaired immune response to infection, and the effect of diabetes on bones, cartilage, tendons and fascial tissue causes mechanical and conformational changes in the architecture of the foot. Gait abnormalities, impaired balance and falls frequently ensue. In advanced peripheral diabetic neuropathy, the patient no longer senses pain developing a loss of the protective sensation (LOPS), the most common component in the pathway to the development of diabetic foot ulcerations (DFU) and Charcot neuroarthropathy.^{6,7,10} Combined with ischemia and infection, LOPS may culminate in amputation. DFUs are responsible for more hospitalizations than any other complication of diabetes with 5% of diabetic patients developing foot ulcers in the U.S. each year and 1% of those patients requiring an amputation.⁸

The pathophysiology for DSPN, as noted above, is complex and involves multiple mechanistic pathways. Hyperglycemia in concert with insulin resistance and abnormal adiposity leads to the accumulation of advanced glycation end products (AGE), toxic effects of free fatty acids and proinflammatory adipokines. These factors damage nerve fibers, effecting initially smaller unmyelinated C-fibers and progressively advancing to damage larger myelinated fibers. Direct axonal injury occurs secondary to endothelial injury, causing endothelial dysfunction and reduction of nitric oxide synthase (NOS) levels, leading to small vascular vasoconstriction, larger vascular calcifications and constriction, which ultimately result in nerve ischemia.^{6,7,8}

Therapeutic intervention for the prevention and treatment of DSPN includes optimized glycemic control, dietary and lifestyle based counselling, antioxidant-rich nutrition, weight management, moderate exercise, routine foot screening, proper foot wear, and avoidance of alcohol and tobacco. Other than tight glycemic control, there are no effective treatments that target the pathophysiology of DSPN. In addition to glycemic control, diabetic neuropathy management has focused predominantly on symptomatic pharmaceutical pain control with analgesics and medications such as pregabalin and duloxetine (FDA approved for the treatment of neuropathic pain from diabetes).³ Pharmacologic agents prescribed for pain from DSPN are listed in Table 3.

Drug Class	Agent	Effective Dose	
Anticonvalgents	Pregabalin	300-600 mg/day	
Anticonvulsants	Gabapentin	900-3,600 mg/day	
Antidepressants (Serotonin-	Duloxetine	60-120 mg/day	
norepinephrine reuptake inhibitors)	Venlafaxine	75-225 mg/day	
	Amitriptyline	25 100 mg/day	
Tricyclic antidepressants (TCA)	Desipramine	23-100 mg/day	
	Nortriptyline		
		210 mg/day	
		Immediate Release:	
Onicida	Tramadol	day 1: 700mg; day 2	
Opiolus	Tapentadol	60 mg/day	
		Extended Release: 50	
		mg twice daily	

 Table 3. Pharmacologic interventions for the treatment of pain associated with DSPN ^{3,4}

*Adapted from Pop-Busui, R, Boulton, AJ. Diabetic Neuropathy: A Position Statement by the American Diabetes Association. Diabetes Care 2017 Jan; 40(1):141-142³

While TCAs are the most studied agents used for neuropathic pain, the use of such agents has occurred in the absence of regulatory approval from the Food and Drug Administration (FDA). Duloxetine (Cymbalta®) and pregabalin (Lyrica®) are medications approved by the FDA specifically for the treatment of painful peripheral diabetic neuropathy. Patients may supplement oral agents with topical therapy- including capsaicin 0.075% cream, doxepin 5% solution or lidocaine 5% patches. Additionally, topical nitrates, alpha-lipoic acid antioxidant, and homeopathic agents such as evening primrose oil have been reported with variable success in reducing neuropathic pain.

In an effort to avoid overuse of opioids for severe unrelenting pain, the American Pain Society and the Academy of Pain Medicine have generated guidelines that include the use of non-pharmaceutical interventions currently used to treat chronic pain, *Clinical Guidelines for the Use of Chronic Opioid Therapy in Chronic Noncancer Pain*. Non-pharmaceutical agents such as electrical nerve stimulation (E-Stim), acupuncture, electro-acupuncture, cognitive behavioral

therapy (CBT), biofeedback, and physical therapy (PT) have some usefulness in treating painful peripheral DSPN.¹¹

Potential Therapeutic Value of Pulsed Electromagnetic Energy Fields (PEMF) for DSPN

Provant[®] Therapy System is a medical device manufactured by Regenesis Biomedical, Inc. (Scottsdale, AZ), that has been cleared by the FDA (K972093, K091791, AND K131979) "for adjunctive use in the palliative treatment of post-operative pain and edema in superficial soft tissue." The device delivers self-administered, non-thermal, non-ionizing pulsed electromagnetic energy to the target tissue, using 27.12 MHz pulses lasting 42 microseconds and delivered 1000 times per second. The system generates an electromagnetic field that is continuously monitored and regulated to ensure consistent dosing. Life Science laboratory research led to Provant Therapy's energetic settings, which have been associated with reductions in post-operative chronic pain in a clinical trial. Provant Therapy is dual-field electromagnetic energy (i.e. high electric and magnetic fields). High energy electric and magnetic fields in combination have been associated with changes in gene expression which are involved in pain and inflammation pathways in laboratory studies.^{23,32} The therapeutic electromagnetic field is delivered by means of an applicator pad that is placed against the treatment site. The device is non-invasive and does not require placement of surface or deep electrodes, nor removal of bandages or clothing. Treatment is usually imperceptible and very well tolerated. Evidence suggests that the Provant[®] Therapy System can reduce pain, promote healing, and promote restored range of motion following reparative surgery in wounded extremities.^{19,21} As an analgesic, it is non-addictive and does not alter the mental state of the user. Regenesis Biomedical, Inc., has marketed the device since 2004 and has treated over 15,000 patients within the U.S. Over two million individual treatments have been administered with rare adverse events reported.¹⁵ In addition, the safety of PEMF has been well documented. The 2012 meta-analysis by Guo et al²⁰ of 25 clinical trials of PEMF in the treatment of pain, edema and wound healing identified no serious adverse events among 1,332 patients treated with PEMF. In addition, the same meta-analysis found statistically significant evidence supporting the efficacy of adjunctive PEMF therapy for pain relief, edema reduction, and wound healing promotion. Finally, adjunctive PEMF therapy has been reported effective in alleviating pain resulting from trauma, 12,14,16,23,25,27 and chronic pain. 13,15,26

In vitro and in vivo evidence suggest PEMF functions by modulating factors involved in pain signaling and soft tissue repair. In vitro studies demonstrated that PEMF treatment of cells in culture can mediate wide-spread changes in transcript levels encoding factors involved in pain and the inflammatory response (including endogenous opioids, growth factors, cytokines, and cell cycle regulating factors),^{20,21,24} and can promote cell proliferation.¹⁷ Regenesis Biomedical, Inc. scientists recently found that PEMF increases endogenous opioid expression, which coincides with an increase in endothelin receptor B in keratinocytes, suggesting that PEMF treatment induces a localized analgesic effect by activation of these receptors by endothelin-1.^{21,22} These findings have led to the proposition that PEMF activates peripheral endogenous opioids which, in turn, activate an analgesic cascade via the endothelin pain axis. In a recent clinical study, PEMF usage for post-

operative pain not only reduced pain levels and opioid consumption relative to sham-treated patients, but was also associated with lower IL-1ß levels in post-operative wound exudates.²⁴ Together, these findings suggest that PEMF therapy reduces pain both by modulating inflammation and by activating peripheral endogenous opioids.

In vitro studies have provided evidence that PEMF therapy improves nerve growth and may improve nerve function through up-regulation of genes involved in neurogenesis (data on file). In addition, genes related to angiogenesis have also been shown to be up-regulated.

An exploratory prospective randomized, sham-controlled study was recently conducted at two sites using the Provant[®] Therapy System to (a) evaluate small fiber nerve growth and function in subjects with painful peripheral diabetic neuropathy and to (b) determine the safety and feasibility of Provant in such subjects. Twenty-three subjects with painful peripheral diabetic neuropathy were treated for 60 days with twice-daily PEMF therapy. Subjects were eligible for enrollment if they had type 2 diabetes with persistent numbness, tingling, or burning in at least one foot despite standard of care treatment.

Nineteen subjects in this study were evaluated for the effectiveness of the Provant[®] Therapy System in enhancing small fiber nerve growth and function. PEMF treatment twice daily for 60 days was associated with improved skin perfusion pressure, and improved nerve conduction velocity, although no consistent changes were observed in self-reported pain scores based on paper diaries. The twice daily application of PEMF was determined to be feasible and safe in subjects with DSPN.

The purpose of the current study is to evaluate the efficacy and safety of PEMF treatment with the Provant[®] Therapy System. The current study focuses on pain relief and self-reported functional improvement as well as objective measures that may further elucidate the basic mechanisms of the intervention. The current study will use electronic diaries rather than paper diaries and include a larger sample size to improve the reliability and precision of the result.

2. STUDY OBJECTIVES

This study is designed to evaluate the efficacy of dual field PEMF Therapy [Provant[®] Therapy System] compared to sham treatment in patients with painful diabetic distal symmetric peripheral neuropathy (DSPN) when treatment is administered, 30 minutes twice daily through a 120-day period (4 months).

3. STUDY DESIGN

3.1 Study Design

Part A of the study is a double-blind, sham-controlled, randomized trial of the safety and efficacy of dual field PEMF therapy in subjects with bilateral symmetrical painful diabetic distal symmetric peripheral neuropathy (DSPN). A graphic presentation of the study design for Part A is shown in Figure 1. Part B of the study is an 8-month open-label active treatment extension period. A graphic presentation of the study design is shown in Figure 2.

Figure 2. Part B Study Flow Schematic

3.2. Efficacy Endpoints

This study will evaluate the changes in NPRS, skin perfusion pressure (SPP), Sural Nerve Conduction Studies (NCS), WPAIQ, NeuroQoL, Patient Global Impression (PGI), thermal sensory perception (QST), and change in nerve density at the distal thigh and distal leg from baseline to 120 days (4 months).

3.3 Safety Evaluation

All observed and reported adverse effects will be recorded by the research staff. Start dates, end dates, frequency, severity of the event, any treatment required to treat the event, and the investigator's judgment on causality and relationship to the study device will be assessed for each AE. Any AE occurring after the signing of the informed consent form will be recorded. Only those AEs occurring after initiation of the first treatment with the study

device will be considered treatment-emergent AEs.

Adverse events will be mapped to preferred terms and body systems using the Medical Dictionary for Regulatory Activities (MedDRA) coding dictionary.

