7.3 Adverse Events

All summaries of adverse events will be based on treatment-emergent adverse events. Adverse events will be provided in a listing. The number and percentage of subjects experiencing adverse events will be summarized. Summaries by maximum severity and relationship to the study device (active or sham) will also be provided. Serious adverse events and adverse events leading to discontinuation from the study will be presented. Treatment-related adverse events will be defined as adverse events with investigator assessment of related or possibly related. In summaries of adverse events by severity and relationship to study device, patients reporting multiple episodes will be counted once under the worst severity and the strongest relationship, respectively. Serious adverse events will also be presented by relationship to treatment. The number of patients with at least one adverse event will be tabulated for each treatment group. The number of adverse events for each treatment group will also be tabulated.

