11. ADVERSE EVENTS AND UNANTICIPATED ADVERSE DEVICE EFFECTS

11.1 Adverse Events

An adverse event is defined as follows: Any untoward medical occurrence in a patient or clinical investigation patient administered a medical device treatment which does not necessarily have to have a causal relationship with this treatment. An AE can therefore be any unfavorable and unintended sign (including an abnormal laboratory finding), symptom, or disease temporally associated with the use of study device treatment, whether or not considered related to the study device.

All AEs occurring after signing of the consent form will be recorded. AEs arising subsequent to the time of initiation of first treatment with study device will be considered treatment emergent AEs.

At each contact with the subject, the investigator or designee must seek information on AEs by nonleading specific questioning and, as appropriate, by examination. All observed or volunteered AEs, regardless of suspected causal relationship to study device, must be recorded in the patient's chart.

Any events involving illnesses or injuries with onset during the study or any events involving exacerbations of pre-existing illnesses should be recorded. All clearly related signs and symptoms should be grouped together and recorded as a single diagnosis in the patient's chart. A pre-existing condition must not be reported as an AE unless the condition worsens during the trial.

Each AE will be independently judged by the investigator in terms of causality. The following definitions will be used for these causality assessments.

Related:	This causal relationship is assigned when the AE:
	• starts a reasonable time after study device administration,
	• cannot be reasonably explained by the subject's clinical state.
Possibly Related:	This causal relationship is assigned when the AE:
	• starts a reasonable time after study device administration, but
	• could have been produced by the subject's clinical state or other modes of therapy administered to the subject.
Unrelated:	This causal relationship is assigned when the AE:
	• is definitely not associated with the study device administered and is readily explained by other events or diagnoses.

Each AE will also be independently judged by the investigator in terms of severity. The following definitions will be used for these severity assessments.

Mild:	The event is transient (<48 hours) or causes mild discomfort; no medical intervention/therapy is required

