11.2 Anticipated Adverse Device Effects Associated with Provant Therapy System

Anticipated adverse events associated with PROVANT® Therapy System are as follows:

- Skin Reaction in the application area (i.e. rash, erythema)
- Altered sensation in the treatment area (i.e. burning, paresthesia)
- Hyperalgesia in the application area (i.e. increased pain, hypersensitivity)

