12.1.2. Summaries of Adverse Events

All summaries of AEs will be based on treatment-emergent AEs and presented using the Level 2 table designs. Adverse events will be coded using the system organ class and preferred term. The number and percentage of subjects experiencing AEs will be summarized by system organ class and preferred term. Summaries by maximum severity and relationship to the study device (active or sham) will also be provided. Serious adverse events and AEs leading to discontinuation from the study will be presented by reported adverse event term.

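### The treatment-emergent definition has no clause for worsening, so a dated AE that starts between consent and the first session can stay out of the AE tables even if it worsens on the device

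*Protocol*

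**What the plan says.** AE collection starts at consent. Protocol 11.1: "All AEs occurring after signing of the consent form will be recorded".

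The treatment-emergent label starts later and depends on onset. In protocol 3.3 the limiting sentence opens "Only those AEs occurring after initiation of the first treatment with the study" device, and protocol 11.1 says "AEs arising subsequent to the time of initiation of first treatment with study device will be considered treatment emergent AEs". Neither mentions an event that begins earlier and then changes in severity or seriousness.

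The SAP gives no fuller definition. SAP 12.1.1 names the AE start date as an input to the treatment-emergent algorithm and to the identification of unique occurrences.

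The label then governs the tables. Protocol 7.3: "All summaries of adverse events will be based on treatment-emergent adverse events". SAP 12.1.2: "All summaries of AEs will be based on treatment-emergent AEs".

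Protocol 11.1 has two sentences on worsening, both about conditions already present: "A pre-existing condition must not be reported as an AE unless the condition worsens during the trial" and "Any events involving illnesses or injuries with onset during the study or any events involving exacerbations of pre-existing illnesses should be recorded".

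**The concern.** Recording starts about two weeks before exposure, and the label that gives entry to the tables looks only at when an event began. A new AE from the run-in that is mild at the first session and severe or serious a month later is a change on treatment, yet its start date lies before treatment.

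The gap matters somewhat more than usual here because the expected device effects resemble the disease. Protocol 11.2 lists, among others, "Altered sensation in the treatment area (i.e. burning, paresthesia"), together with skin reactions and increased pain in the application area. Protocol Table 2 gives burning pain and tingling as symptoms of DSPN. Heat-pain testing on the foot, which is the treated area, takes place at the Enrollment Visit before the first session. An event of this type could therefore begin before exposure and be aggravated by it. At stake is whether the by-arm AE tables would show that aggravation.

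**Working it through.** The documents state no figure to reproduce, so the check is mainly a matter of following one event through the rules.

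**Tracing the event.** Take an AE that was not present at consent, starts on a known date before the first session, and becomes severe or serious on the device.

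1. It is recorded, because collection starts at consent (protocol 3.3 and 11.1).
2. It is not treatment-emergent under protocol 3.3 or 11.1, because it began before the first session.
3. The pre-existing-condition sentences in protocol 11.1 do not clearly reach it. They do not say whether pre-existing means before consent or before the device.
4. No passage says that a worsened AE gets a new record or a new start date. Protocol 11.1 asks for clearly related signs and symptoms to be grouped under one diagnosis, which leans towards a single record.
5. The maximum-severity rule in SAP 12.1.2.2 does not bring it back, because that table too is built on treatment-emergent events only.
6. The missing-date rule in SAP 12.1.1 does not apply, because the date is known.

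**Where it would and would not appear, if kept as one record**

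| Output | Shown? | Reason |
|---|---|---|
| Tables 14.3.1.1 to 14.3.1.4 and 14.3.2 | No | All AE summaries use treatment-emergent AEs (SAP 12.1.2) |
| Listing 16.2.7.3 (AEs leading to discontinuation) | No | Restricted to treatment-emergent AEs (SAP 12.1.2.4) |
| Listings 16.2.7.1 and 16.2.7.2 (all AEs; SAEs) | Can be | No such restriction is stated (SAP 12.1.2.3, 12.1.2.5) |
| Table 14.1.1 (reasons for early termination) | Yes, if withdrawn | By-arm counts with no such restriction (SAP 8, Level 1 layout in SAP 7) |

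**A side effect of SAP 12.1.1.** An AE with a missing or inadequate partial start date counts as treatment-emergent unless it is known to have ended before the study began. That reference point is not the first treatment. A run-in event with a poorly recorded date can therefore enter the tables, while a well-dated one that worsens does not.

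**Length of the window.** Screening is Day -15 and the first session is on the morning of Day 1 (protocol 4.1, 3.10). Days -15 to 0 make 16 days, against 120 treatment days:

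- nominal: 16 / (16 + 120) = 11.8%
- screening at Day -14: 15 / (15 + 120) = 11.1%
- screening at Day -17: 18 / (18 + 120) = 13.0%

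These are shares of Part A calendar time, not shares of events lost.

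**Illustration of size.** The documents give no rate for AEs that start in this window and later worsen. Purely as assumptions, rates of 1%, 3% and 5% of the 170 subjects give 170 × 0.01 = 1.7, 170 × 0.03 = 5.1 and 170 × 0.05 = 8.5 subjects over both arms.

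**The case against.** The case for leaving the text alone has real force.

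- **The commonest example is already covered.** Every subject enters with at least 6 months of daily neuropathic pain (inclusion criterion 2). Burning, tingling or pain from the disease is then normally the pre-existing condition. Its worsening is an AE in its own right under protocol 11.1, and a treatment-emergent one if dated at the worsening. This stands, and it confines the gap to events that first appear after consent.
- **Day 0 adds little.** Treatment starts the next morning, so that part of the window lasts less than a day. The biopsies are on the distal leg and thigh, away from the applicators under the foot. This stands.
- **Eligibility is reviewed again at the Enrollment Visit.** Exclusions 22 and 25 (confounding pain, skin conditions of the feet) would keep out some subjects with new run-in events. This stands in part.
- **Separate records may be intended.** SAP 12.1.1 speaks of unique occurrences and SAP 12.1.2.2 of multiple occurrences, and CRF instructions that are not in these documents could settle the matter. This is possible, but neither passage says that a worsened event becomes a new occurrence, so the gap remains in the text.
- **The same rule applies to both arms.** Events before exposure are balanced in expectation by randomisation. This stands, so the direction of any bias is conditional.

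A reader might infer that such events vanish from every by-arm safety table. The documents do not support that: Table 14.1.1 counts withdrawals for AEs by arm without the restriction. A reader might also take the 12% as the share of AEs lost. It is a share of calendar time, and only the unknown fraction of those events that later worsens is affected.

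**Conclusion.** The gap is real but narrow, and the point is minor. As written, an AE that first starts between consent and the first session, has a known start date and is kept as one record is absent from Tables 14.3.1.1 to 14.3.1.4, Table 14.3.2 and Listing 16.2.7.3, even if it worsens or becomes serious on the device. It can still be found in the general and SAE listings, and a withdrawal it causes is counted by arm.

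The conclusion rests on two readings that the documents leave open: that the pre-existing-condition text in protocol 11.1 does not extend to AEs starting after consent, and that a worsened AE keeps its record and date. The number of such events cannot be estimated from the documents and is probably small. It would be tempting to conclude that harm in the active arm is understated. That follows only if the device aggravates such events, which the documents do not show. The efficacy analyses and the sample size are not touched.

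**What to change.** - In protocol 3.3 and 11.1 and in SAP 12.1, define a treatment-emergent AE as one that starts, or increases in severity or becomes serious, at or after the first session.
- State that the worsening is recorded as a new entry dated at the worsening, and that this entry feeds Tables 14.3.1.1 to 14.3.1.4, Table 14.3.2 and Listing 16.2.7.3.
- In SAP 12.1.1, make the first treatment the reference point for missing and partial dates, in place of study start.

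The cost is a wording change in two documents, one CRF completion instruction and minor programming. Slightly more events will be counted in both arms.
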